10.3.2.7. Time to CR/CRh

Time to CR/CRh will be summarized using descriptive statistics as assessed from the date of first dose to the date of first response (CR or CRh) in subjects with documented CR/CRh in FAS for the combined Phase 1, Phase 2, and the combined Phase 1/2. Time to CR/CRh will also be summarized by cycle.

10.4. Subgroup Analysis

Appropriate subgroup analyses for ORR and DOR, CRR, CR/CRh rate, CR/CRi/CRp rate, and OS based on the following variables in the combined Phase 1, Phase 2, and the combined Phase 1/2 R/R AML will be provided using the FAS if data are available and/or clinically meaningful. TTR and TTBR will be summarized by best response by investigator assessment, and transfusion independence rate will be summarized by best response by both investigator and IRAC assessments. The ORR, CRR, CR/CRh rate and CR/CRi/CRp rate by subgroups will be presented in forest plots.

1. Age groups (<60, 60 - <70, 70 - <75, ≥75 years)
2. Gender (male vs female)
3. Region (US vs non-US)
4. Race (white vs non-white)

5. Baseline ECOG PS (Grade 0, 1, 2)
6. Number of prior AML therapies (1, 2, >=3)
7. Prior history of MDS (yes vs no)
8. WHO classification of AML (AML with Recurrent Genetic Abnormalities, AML with Myelodysplasia-Related Changes, Therapy related Myeloid Neoplasms, AML not Otherwise Specified)
9. Prior HSCT for AML (yes vs no)
10. IDH2 gene mutation type (R140 vs R172) for ORR and all secondary endpoints
11. Baseline cytogenetic risk status (poor, intermediate, favorable)
12. Best response by Investigator assessment
13. Best response by IRAC
14. Refractory/Relapse status (primary refractory vs relapse; for combined Phase 1/2 only).
15. R/R AML subtypes (subjects who relapse after allogeneic transplantation; subjects in second or later relapse; subjects who are refractory to initial induction or re-induction treatment; subjects who relapse within 1 year of initial treatment, excluding subjects with favorable-risk status according to National Comprehensive Cancer Network [NCCN] Guidelines [NCCN v1.2015]. Favorable-risk cytogenetics: inv(16), +(16;16), t(8;21), t(15;17); subjects who have failed 2 or more cycles of first line therapy [consisting of an intermediate intensity chemotherapy, hypomethylating agent, or low dose cytarabine]; for combined Phase 1/2 only).

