### **12.3. Procedures for Handling Missing, Unused, and Spurious Data**

No imputation will be performed for missing data elements.

When tabulating AE data, partial dates will be handled as follows. If the day of the month is missing, the onset day will be set to the first day of the month unless it is the same month and year as study treatment. In this case, in order to conservatively report the event as treatment emergent, the onset date will be assumed to be the date of treatment. If the onset day and month are both missing, the day and month will be assumed to be January 1, unless the event occurred in the same year as the study treatment. In this case, the event onset will be coded to the day of treatment in order to conservatively report the event as treatment emergent. A missing onset date will be coded as the day of treatment.

For the purposes of reporting, subjects continuing to receive study drug will have time-to-event data (e.g., duration of response and EFS) censored at the date of last documented disease assessment prior to the data cutoff date. Further details of censoring rules will be documented in the statistical analysis plan.

Subjects who have disease progression and continue to receive treatment after progression will be considered as having documented progressive disease at the time of first progression and will be counted as progressive disease at that time in primary efficacy analyses. All response assessments occurring after documented progression will be listed and analyzed separately.

Subjects who discontinue AG-221 treatment to receive HSCT will remain on study and will be followed until documented disease progression or end of study.

Subjects with a best overall response of 'Unknown' or 'Not Evaluable' will be considered non-responders in estimating response rates in the efficacy analysis.

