10.2. Analysis of Primary Efficacy Endpoint

The primary efficacy endpoint of ORR is defined as the rate of responses including CR, CRi, CRp, PR, mCR (for MDS) and MLFS (for AML) by investigator assessment. The ORR will be summarized by the percentage of responses primarily in the FAS with 2-sided exact binomial 95% CI.

Response will also be summarized by the best objective response following the hierarchical order of CR, CRi/CRp, PR, mCR/MLFS, stable disease, relapse/progressive disease/failure, and not evaluable (NE).

An observed ORR in the pivotal Phase 2 R/R AML FAS subjects with the lower bound of the exact binomial 95% CI greater than 25% is deemed clinically meaningful and exceeds the expected ORR with other available therapies. This will be considered as evidence of clinically significant activity of AG-221. The analyses in the combined Phase 1/2 R/R AML on total daily dose of 100mg utilize larger population and thus provide robust estimate of ORR to better describe the clinical activity of AG-221.

To assess the robustness of the primary analysis, the following sensitivity analyses will be performed:

- (1) ORR in the EAS for the combined Phase 1, Phase 2, and the combined Phase 1/2;

- (2) The ORR assessed by Independent Response Adjudication Committee (IRAC) in the FAS for Phase 1, Phase 2, and the combined Phase 1/2 R/R AML.

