Death from indeterminate cause	Deaths occurring before completion of therapy, or < 7 days following its completion; or deaths occurring ≥ 7 days following completion of initial therapy with no blasts in the blood, but no bone marrow examination available
Relapse (defined only for subjects who have previously attained CR, CRi, CRp or MLFS)	Bone marrow blasts ≥ 5 percent; or reappearance of blasts in the blood; or development of extramedullary disease

Source: ([Cheson, et al. 2003](#))

Footnotes on next page

- * All criteria need to be fulfilled; marrow evaluation should be based on a count of 200 nucleated cells in an aspirate with spicules; if ambiguous, consider repeat exam after 5 to 7 days; flow cytometric evaluation may help to distinguish between persistent leukemia and regenerating normal marrow; a marrow biopsy should be performed in cases of dry tap, or if no spicules are obtained; no minimum duration of response required.
- The criterion of CRi is of value in protocols using intensified induction or double induction strategies, in which hematologic recovery is not awaited, but intensive therapy will be continued. In such protocols, CR may even not be achieved in the course of the entire treatment plan. In these instances, the overall response rate should include CR and CRi patients. Some patients may not achieve complete hematologic recovery upon longer observation times.
- Δ This category may be useful in the clinical development of novel agents within Phase I clinical trials, in which a transient morphologic leukemia-free state may be achieved at the time of early response assessment.
- ◇ Four studies showed that failure to convert to a normal karyotype at the time of CR predicts inferior outcome.
- § As an example, in core-binding factor AML low-level polymerase chain reaction-positivity can be detected in patients even in long-term response. Normalizing to 104 copies of ABL1 in accordance with standardized criteria, transcript levels below 10 to 12 copies appear to be predictive for long-term response.

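### If OS is shown by best response, which SAP 10.4 permits, Kaplan-Meier curves from first dose carry guarantee-time bias toward responders

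*SAP*

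**What the plan says.** SAP 10.4 sets out "Appropriate subgroup analyses for ORR and DOR, CRR, CR/CRh rate, CR/CRi/CRp rate, and OS based on the following variables" for the combined Phase 1, Phase 2 and combined Phase 1/2 R/R AML subjects. These "will be provided using the FAS if data are available and/or clinically meaningful". Item 12 of the list is best response by the Investigator and item 13 is "Best response by IRAC". Neither item is limited to particular endpoints, although items 10, 14 and 15 carry qualifiers of their own. The sentence after the list of outcomes says that "TTR and TTBR will be summarized by best response by investigator assessment", and adds transfusion independence by both assessments. It does not mention OS.

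SAP 10.3.1.5 counts OS from first dose and estimates it by Kaplan-Meier, with rates at 3, 6, 9 and 12 months. The only sensitivity analysis censors at HSCT. Protocol 10.8.2 puts the first Phase 2 response assessment at C2D1, with further assessments every 28 days through at least Cycle 12. Best response has no time limit.

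Three places bear on subjects without an evaluable response:
- SAP 10.2 makes not evaluable (NE) the last level of best objective response, separate from the level that contains failure.
- Protocol 12.3 says that Unknown and NE subjects "will be considered non-responders in estimating response rates in the efficacy analysis".
- Table 6 in SAP 15.3 lists "Deaths occurring before completion of therapy" under treatment failure.

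SAP 10.4 refers to none of these.

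**The concern.** Best response is known only after first dose. A subject who dies before responding cannot be a responder, so every responder is certain to be alive from first dose to the response date. Kaplan-Meier curves from first dose credit that time to the responder group. They can therefore separate even when response has no bearing on survival. Censoring at HSCT does not touch this, and the fixed-time rates in SAP 10.3.1.5 are read from first dose, so they are not landmark analyses. Protocol 10.8.3 expects that responses to this class may come later than with cytotoxic drugs, and later responses lengthen the guaranteed time.

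OS is a key secondary endpoint in a study with no control arm, so curves split by response are easily read as showing that response prolongs life. The plan gives no method for separating the part of the gap that comes from how the groups are defined.

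**Working it through.** **1. The plan's own figure.** Protocol 12.1 gives 42/125 = 33.6% with exact 95% CI 25.4% to 42.6%. The beta quantiles are Beta(0.025; 42, 84) = 25.40% and Beta(0.975; 43, 83) = 42.60%, so the figure reproduces. It supplies the ORR used below. Neither document gives a figure for OS by response.

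**2. Null model for Phase 2.** Assumptions not in the documents: OS exponential with median m = 6, 9 or 12 months; response has no effect on death; all responses fall at one visit r. With months = days/30.4, C2D1 is 28/30.4 = 0.92, C3D1 is 1.84 and C5D1 is 3.68 months. Let S(t) = 2^(−t/m) and p = 0.336.
- Responders: S_R(t) = min(1, S(t)/S(r)), so their median is r + m.
- Non-responders, deaths before C2D1 set apart as NE: [S(t) − p·S_R(t)] / [S(C2D1) − p].
- All non-responders pooled: [S(t) − p·S_R(t)] / (1 − p).

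**3. One case in full (m = 9, response at C3D1).** S(C2D1) = 0.9315 and S(C3D1) = 0.8677. The responder median is 1.84 + 9 = 10.84. For t after C3D1 the numerator is S(t) × (1 − 0.336/0.8677) = 0.6128·S(t).
- NE apart: 0.6128/0.5955 = 1.029, so S(t) = 0.486 and t = 9.37. Gap 1.47 months.
- Pooled: 0.6128/0.664 = 0.923, so S(t) = 0.542 and t = 7.96. Gap 2.88 months.

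**4. All cases (medians in months).**

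| m | Response at | Responders | NE apart | Gap | Pooled | Gap |
|---|---|---|---|---|---|---|
| 6 | C2D1 | 6.92 | 6.92 | 0.0 | 5.49 | 1.4 |
| 6 | C3D1 | 7.84 | 6.32 | 1.5 | 4.89 | 3.0 |
| 6 | C5D1 | 9.68 | 4.72 | 5.0 | 3.49 | 6.2 |
| 9 | C2D1 | 9.92 | 9.92 | 0.0 | 8.51 | 1.4 |
| 9 | C3D1 | 10.84 | 9.37 | 1.5 | 7.96 | 2.9 |
| 9 | C5D1 | 12.68 | 8.06 | 4.6 | 6.64 | 6.0 |
| 12 | C2D1 | 12.92 | 12.92 | 0.0 | 11.51 | 1.4 |
| 12 | C3D1 | 13.84 | 12.39 | 1.5 | 10.99 | 2.9 |
| 12 | C5D1 | 15.68 | 11.19 | 4.5 | 9.79 | 5.9 |

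Deaths before C2D1 are 10.1%, 6.8% and 5.2% at m = 6, 9 and 12. Of 125 subjects that is between 125 × 5.2% = 6.5 and 125 × 10.1% = 12.6.

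**5. Other ORR values.** At 25.4% and 42.6%, the NE-apart gap stays 0.0 at C2D1 and spans 1.3 to 1.8 months at C3D1 and 3.9 to 6.1 at C5D1.

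**6. Separate check with response times spread over visits.** In a null simulation of 400,000 subjects per scenario, the same three values of m were crossed with latent median response times of 1, 2 and 3 months, with non-responders pooled. The naive hazard ratio was 0.57 to 0.84, favouring responders in all nine scenarios. With response treated as time-dependent, the death-rate ratio was 0.99 to 1.00.

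**7. A single null trial.** With 125 subjects, assumed follow-up uniform over 12 to 36 months and 2,500 trials per scenario, the responders' median was the higher one in the following shares of trials:
- C2D1: 49% to 52% (NE apart) or 67% to 82% (pooled).
- C3D1: 65% to 82% or 80% to 98%.
- C5D1: 91% to 100% or 97% to 100%.

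**The case against.** The strongest reply is that the display may never exist. One variable list serves six outcomes and cannot be fully crossed, since ORR by best response is true by definition. Items 12 and 13 have a natural use for DOR, and OS is absent from the sentence that names what is summarised by best response. This stands as far as it goes. A reader might infer that the SAP commits to OS by best response, and the text does not support that. But OS is on the list and items 12 and 13 are not limited, so the pairing is allowed.

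A reader might also infer that the plan has no rule at all for NE subjects. That is too strong: SAP 10.2 and Protocol 12.3 each give one, the latter for response rates only. What is missing is which convention governs this display. Table 6 adds a third possible home for early deaths, under failure, which neither model above represents.

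The pooled figures describe a responder versus non-responder split that SAP 10.2 does not define. It has seven levels, and the NE-apart figures are the closer match. C5D1 for every response is a stress case. Phase 1, first assessed at C1D15 (Protocol 10.8.1), is not modelled. These points limit what can be said about size. They do not alter the mechanism.

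The plan also reports 30-day and 60-day death rates (SAP 11.3) and response timing by cycle (SAP 10.3.2.4 and 10.3.2.5). These help a reader judge the curves but do not correct them.

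**Conclusion.** The point holds in conditional form. If OS by best response is produced by the method in SAP 10.3.1.5, the curves favour responders for reasons of definition. In the model the bias vanishes only when all responses come at the first assessment and earlier deaths are shown apart.

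Its size cannot be known from the documents, which give neither median OS nor response times. The modelled gaps run from 0.0 to 5.0 months with early deaths apart and from 1.4 to 6.2 months pooled, at ORR 33.6%. They rest on exponential survival with a median of 6 to 12 months and no effect of response.

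It would be wrong to infer that the pivotal conclusion is compromised. The display is descriptive, no test between response groups is planned, and neither the 42/125 criterion nor OS in the whole FAS depends on it. This is an optional, low-severity improvement.

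**What to change.** In SAP 10.4, exclude items 12 and 13 for OS; they can stay for DOR. If OS by response is wanted, show any response versus none with response as a time-dependent covariate, for example as Simon-Makuch curves. No test is needed. The first-response dates are already derived for TTR, by Investigator and by IRAC. A display by response category would use the category-specific dates behind TTBR and TTCR, moving a subject into a category only when it is reached.

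If plain curves by best response are kept, state how NE subjects and deaths before the first assessment are grouped. Footnote the curves as descriptive and subject to guarantee-time bias.

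The cost is SAP wording and no new data: at least one sentence and one footnote. The time-dependent version replaces up to six displays (2 assessors × 3 populations). The downside is slightly more analysis work and less familiar curves. The method removes immortal time. It does not remove prognostic differences between responders and non-responders, and the text beside the curves should say so.

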11. SAFETY ANALYSIS

Unless specified otherwise, the safety data will be summarized and presented by subject groups as described in items 1 to 5 of [Section 5.1](#) for the SAS. In the analysis for MTD, DLT will be summarized for subject in the DDS by assigned dose groups for Phase 1 dose escalation.

11.1. Adverse Events

Adverse events will be analyzed in terms of treatment-emergent adverse events (TEAEs), which are defined as any AEs that begin or worsen on or after the start of study drug through 28 days after the last dose of study drug. All AEs will be coded using MedDRA version 20.0. The severity will be graded based on NCI CTCAE version 4.03.

A treatment-related TEAE is defined as TEAE that is suspected (possibly or probably related) by the Investigator to be related to the study drug. The incidence of TEAEs will be summarized by MedDRA SOC and PT. The intensity of AEs will be graded 1 to 5 according to the NCI CTCAE version 4.03. For all other AEs not described in the CTCAE criteria, the intensity will be assessed by the Investigator as mild (Grade 1), moderate (Grade 2), severe (Grade 3), life-threatening (Grade 4) or death (Grade 5). The Grade 3-4 TEAEs will also be summarized by MedDRA SOC and PT. If a subject experiences the same AE more than once with different toxicity grade, then the event with the highest grade will be tabulated in “by grade” tables. If a subject experiences multiple AEs under the same PT (SOC), then the subject will be counted only once for that PT (SOC).

Analysis of TEAEs of special interest will be presented for combined Phase 1, Phase 2 and the combined Phase 1/2 as described in items 3 to 5 of [Section 5.1](#). Some special interested PTs will be grouped and the TEAEs will be summarized by Grouped Terms and be presented for combined Phase 1/2 as described in item 5 of [Section 5.1](#).

The number of subjects with at least one TEAE will be summarized. Analysis for all TEAEs and Grade 3-4 TEAEs by descending frequency of PT will also be summarized. Tabulations of overall summary of TEAEs, all TEAEs by SOC/PT and Grade 3-4 TEAEs will be summarized by cycles for combined Phase 1, Phase 2, and the combined Phase 1/2. All TEAEs and Treatment-related TEAEs leading to study drug discontinuation, reduction or interruption will be summarized separately. Tables summarizing the incidence of TEAEs will be generated for each of the followings:

1. Overall summary of TEAEs.
2. All TEAEs by SOC and PT.
3. Treatment-related TEAEs by SOC and PT.
4. All TEAEs by descending frequency of PT in total column.
5. All TEAEs with Grade 3-4 by SOC and PT.
6. TEAEs by maximum severity.
7. Treatment-related Grade 3-4 TEAEs by SOC and PT.
8. All TEAE with Grade 3-4 by descending frequency of PT in total column.

9. All serious TEAEs by SOC and PT.
10. All serious TEAEs by decreasing frequency of PT in total column.
11. Treatment-related serious TEAEs by SOC and PT.
12. TEAEs leading to study drug permanently discontinued.
13. Treatment-related TEAEs leading to study drug permanently discontinued.
14. TEAEs leading to study drug dose reduced.
15. Treatment-related TEAEs leading to study drug dose reduced.
16. TEAEs leading to study drug dose interrupted.
17. Treatment-related TEAEs leading to study drug dose interrupted.
18. TEAEs leading to death.
19. Treatment-related TEAEs leading to death.

Appropriate safety subgroup analysis will be presented for the combined Phase 1, Phase 2 and combined Phase 1/2 by total daily dose for R/R AML subjects and by malignancy type as described in item 3 and 5 of [Section 5.1](#). All TEAEs by SOC/PT and the overall TEAE summary table for the following subgroups will be provided when the numbers of subjects are sufficient:

- Age (<60, 60 - <75, ≥75 years)
- Sex (Male vs Female)
- Race (White vs Non-white)
- Region (US vs France)
- WHO classification if AML (AML with Recurrent Genetic Abnormalities, AML with Myelodysplasia-Related Changes, Therapy related Myeloid Neoplasms, AML not Otherwise Specified)
- Baseline ECOG (Grade 0, 1, 2)
- Baseline creatinine clearance (<45, 45-<60, ≥60 mL/min)
- Baseline ANC value ($\leq 0.5 \times 10^9/L$, $0.5 < 1 \times 10^9/L$, $\geq 1 \times 10^9/L$)

Summary of all TEAE, Grade 3-4 TEAE, and Grade 3-4 infection, bleeding and all grade febrile neutropenia by the response period and by study period will be summarized in R/R AML for the combined Phase 1, Phase 2, and combined Phase 1/2 to summarize clinical benefit. DLTs will be summarized for Phase 1 dose escalation by assigned dose group in the DDS.

All TEAEs will be listed by subject. Listings for non-treatment-emergent AEs, DLTs, discontinuations due to AE, AEs for re-enrolled subjects, TEAEs leading to death, TEAEs leading to dose reduction, and SAEs will also be provided.

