5. GENERAL STATISTICAL CONSIDERATIONS

5.1. Reporting Conventions

Tabulations will be produced for subject disposition, demographic and baseline disease characteristics, safety, and clinical activity parameters. The study data will be analyzed and reported for efficacy/safety when applicable based on all subjects' data from the Phase 1 dose escalation, the Part 1 Expansion, the combined Phase 1, Phase 2, and the combined Phase 1/2 up to the data cut-off date of 29 July 2019.

Unless specified otherwise, the data will be presented as specified below:

1. In Phase 1 dose escalation, all subjects (combining different malignancy types [overall]) will be utilized. Data will be summarized by total daily dose groups, unless otherwise specified. The total daily dose is defined as the total dose a subject receives during a day based on the assigned or actual dose regimens for efficacy and safety, respectively.
2. In Part 1 Expansion, all subjects (combining different malignancy types) will be utilized and will be grouped into 4 arms (groups):
 - Arm 1: R/R AML and age ≥ 60 years, or any subject with AML regardless of age who has relapsed following a BMT.
 - Arm 2: R/R AML and age < 60 years, excluding subjects with AML who have relapsed following a BMT.
 - Arm 3: Untreated AML and age ≥ 60 years that decline standard of care chemotherapy.
 - Arm 4: IDH2-mutated advanced hematologic malignancies not eligible for Arms 1 to 3.
3. In the combined Phase 1, analyses will be presented by total daily dose groups as < 100 mg, 100 mg and > 100 mg for subjects with R/R AML. The overall subjects in the combined Phase 1 will be summarized by malignancy type including R/R AML, untreated AML, MDS, and other.
4. In Phase 2, data will be summarized primarily for all R/R AML subjects.
5. In the combined Phase 1/2, R/R AML will be presented by total daily dose groups as < 100 mg, 100 mg and > 100 mg, and the overall subjects will be presented by malignancy type.

For subjects who were discontinued from study treatment, underwent HSCT, and then re-started AG-221, data after restarting AG-221 will be excluded from all summary analyses except for death. The data collected after restarting AG-221 will be provided in listings.

Categorical variables will be summarized by frequency distributions (number and percentages of subjects) and continuous variables will be summarized by descriptive statistics (number of subjects, mean, standard deviation (SD), median, minimum, and maximum).

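### The SAP 11.1 clinical-benefit tables by response and study period have no person-time denominator, leave both periods undefined, and exclude Grade 5 from their severe-event rows

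*SAP*

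**What the plan says.** After its list of standard tables, SAP 11.1 states that "Grade 3-4 infection, bleeding and all grade febrile neutropenia by the response period and by study period will be summarized in R/R AML", in a sentence that also takes in all TEAEs and Grade 3-4 TEAEs. These cover R/R AML in the combined Phase 1, Phase 2 and combined Phase 1/2 groups. The stated aim is "to summarize clinical benefit", so the tables are meant to carry a message about benefit as well as to describe safety. Protocol 6.4.3.2 and 12.5.7 likewise list infection rates among the measures of clinical activity, without a denominator.

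The sentence names no statistic, and the visible text defines neither period. The conventions that would apply are these:

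- SAP 5.1: "Categorical variables will be summarized by frequency distributions (number and percentages of subjects".
- SAP 11.1, for a subject with several AEs under one term: "then the subject will be counted only once for that PT (SOC".
- SAP 11.1, for the standard severe-event table: "The Grade 3-4 TEAEs will also be summarized by MedDRA SOC and PT".

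On severity, the SAP 11.1 scale ends with "life-threatening (Grade 4) or death (Grade 5", so death is a grade of its own outside the 3-4 band. If the same AE recurs at different grades, "then the event with the highest grade will be tabulated in" the by-grade tables. Fatal TEAEs appear in items 6, 18 and 19 of the SAP 11.1 list and in a listing, and SAP 11.3 tabulates causes of death. None of these is split by response or study period.

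**The concern.** A table meant to show that patients in response have fewer infections or bleeds invites a comparison between periods. The percentage of subjects with at least one event rises with the time observed. If the periods differ in length, the percentages differ even when the underlying risk is the same, and a real change in risk can be masked.

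The grade limit raises a second problem. A fatal infection is the outcome such a table should least miss, yet a Grade 3-4 row does not count it. If fatal events fall unevenly across the periods, the severe-event contrast is distorted in a way the row does not show. What is at stake is the interpretation of supportive descriptive tables. The primary endpoint is not affected.

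**Working it through.** **Figures in the documents.** Neither document gives an event rate, period length or expected count for these tables, so there is no stated figure to reproduce. All rates, lengths and event counts below are assumptions. The documents supply only the time unit (28-day cycles, SAP 15.4) and the Phase 2 size (about 125, SAP 4.4).

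**Do the periods differ in length?** This is inferred, not stated. SAP 11.2 groups time to response as under 2, 2 to under 4, and 4 or more cycles, so time before response differs between subjects. The TEAE window in SAP 11.1 closes 28 days after each subject's final dose, so total time also differs. Non-responders have no time in response.

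**Effect of length at a constant rate.** Percentage with at least one event = 1 − exp(−rate × cycles).

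| Rate per cycle (assumed) | 2 cycles | 6 cycles | Difference |
|---|---|---|---|
| 0.05 | 1 − exp(−0.10) = 9.5% | 1 − exp(−0.30) = 25.9% | 16.4 points |
| 0.10 | 1 − exp(−0.20) = 18.1% | 1 − exp(−0.60) = 45.1% | 27.0 points |
| 0.20 | 1 − exp(−0.40) = 33.0% | 1 − exp(−1.20) = 69.9% | 36.9 points |

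In every row the rate per subject-cycle is the same in both periods.

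**Effect of length when response truly halves the rate.** Assume 0.20 per cycle for 2 cycles before response, which gives 33.0%, then 0.10 per cycle in response.

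| Cycles in response | Percentage in response | Contrast with 33.0% |
|---|---|---|
| 2 | 1 − exp(−0.20) = 18.1% | benefit shown |
| 4 | 1 − exp(−0.40) = 33.0% | benefit hidden |
| 6 | 1 − exp(−0.60) = 45.1% | benefit reversed |
| 8 | 1 − exp(−0.80) = 55.1% | benefit reversed |

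The rate ratio is 0.5 throughout.

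**Effect of omitting Grade 5.** Assume 30 of 125 subjects have a Grade 3-4 infection (30/125 = 24.0%) and a further 3, 6 or 12 have a fatal one.

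| Added fatal cases | Grade 3 or higher | Share missed by the Grade 3-4 row |
|---|---|---|
| 3 | 33/125 = 26.4% | 3/33 = 9.1% |
| 6 | 36/125 = 28.8% | 6/36 = 16.7% |
| 12 | 42/125 = 33.6% | 12/42 = 28.6% |

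If the highest-grade rule is applied to these tables, a subject whose Grade 3-4 infection recurs fatally under the same term would also leave the Grade 3-4 count. The SAP does not say whether the rule applies here.

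**The case against.** The case on the other side has several parts.

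- **The method is not stated.** A reader might infer that the SAP prescribes crude percentages and a formal comparison between periods. It does neither. The percentages follow from the general defaults, no test is planned, and SAP 10.1 describes the efficacy analyses as estimation. Protocol 12.5.4, on exposure and safety, is redacted and could mention rates. This limits how firmly the point can be put. SAP 11.1 is the visible specification of these tables, though, and it gives no other denominator.
- **Unequal length is not stated either.** Study period could mean fixed windows, in which case the length argument would not apply to that half of the tables. This stands, and it shows that the missing definitions are the more basic gap.
- **Fatal events are not lost.** A reader might infer that fatal infections and bleeds drop out altogether. They do not: the same sentence plans all TEAEs by period, which includes Grade 5, and fatal TEAEs and deaths are tabulated elsewhere. Febrile neutropenia is planned at all grades. Whether the Grade 3-4 limit governs bleeding is unclear from the grammar. What remains is that no dedicated severe-infection or fatal-event table by period counts them.
- **Related tables exist.** SAP 11.1 plans TEAE tables by cycle, in windows of nominally equal length, and SAP 9.1 tabulates exposure by best response. They help with context, but the by-cycle tables are not split by response status, and the exposure tables give no time within each period.
- **The sizes are hypothetical.** This is correct. They show what can happen, not what will be observed.

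**Conclusion.** The point holds as a gap in specification. As the visible text stands, the period tables would default to percentages of subjects over undefined periods with no person-time denominator. Under the assumed rates and lengths, length alone produces differences of about 16 to 37 points, and a true halving of the rate can be shown, hidden or reversed. The Grade 3-4 TEAE and infection rows (and bleeding, if limited to that band) exclude Grade 5. In the assumed counts, the infection row would miss 9% to 29% of subjects with an infection of Grade 3 or higher.

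A reader might conclude that the tables are biased in favour of AG-221. The documents do not support a direction: a longer response period makes the percentages understate benefit, and a shorter one makes them overstate it. The conclusion rests on the SAP 5.1 and 11.1 defaults applying to these tables and on time in response varying between subjects, which SAP 11.2 makes a safe inference.

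**What to change.** Amend SAP 11.1 as follows:

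1. Define response period and study period: start, end, how non-responders are handled, and where time after relapse is placed.
2. Beside the existing n (%), report for each period the number of events and the number of subjects with a first event per subject-time at risk, each with a 95% CI.
3. Use Grade 3 or higher, including Grade 5, for severe TEAEs and for infection.
4. State the grade scope for bleeding. If it is meant to be severe bleeding, use Grade 3 or higher including Grade 5.

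Add a note that the rates adjust for length of observation only. They do not make responders comparable with non-responders, since a subject must survive to response to contribute time in it.

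The cost is SAP wording and some programming. The dosing, response and AE dates are already collected, and the planned percentages can stay.
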